### *Participants*

AUD patients of both genders were successively recruited between June of 2015 and January of 2018 from three specialized clinics for drug dependence treatment, one public and two privates, from the State of Espírito Santo, Brazil. These specialized services applied standard protocols for the treatment of drug addiction, consisting of psychosocial approaches –conducted by a professional team of psychologists, nurses, social workers and physicians, and pharmacotherapy, including benzodiazepines, vitamin B, disulfiram and, when necessary, antidepressants, anxiolytics, antihypertensive, and gastric medications, and folic acid. Two dropouts occurred after randomization. One dropout had to be hospitalized due to clinical instability and another missed many stimulation sessions.

The inclusion criteria for this study were: (1) male and female patients over the age of 18 years; (2) met criteria for alcohol dependence according to the Classification of Mental and Behavioral Disorders (ICD-10) and the Diagnostic and Statistical Manual of Mental Disorders, fifth edition (DSM-5), as determined by clinical evaluation; (3) in stable clinical condition with no need for emergency care; (4) able to read, write, and speak Portuguese; and (5) without severe withdrawal signs or symptoms at baseline.

Exclusion criteria included: (1) a condition of intoxication or withdrawal due to a substance other than alcohol, (2) unstable mental or medical disorder or substance abuse or addiction other than alcohol dependence, except nicotine and/or caffeine or history of marijuana use during adolescence; (3) diagnosis of epilepsy, convulsions, or delirium tremens during the abstinence of alcohol; (4) a previous history of drug hypersensitivity or adverse reactions to diazepam or other benzodiazepines and haloperidol; (5) any contraindication for electrical brain stimulation procedures such as electronic or metal implants.

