#### *Craving assessment: 5-items OCDS*

Craving was scored with a brief scale composed of 5 items (1, 2, 4, 5, and 13) from the Obsessive-Compulsive Drinking Scale (OCDS) (21-23), which assesses craving in a narrow sense according to De Wildt et al. (24).

Questions of this brief scale allow quantification of thoughts and feelings (obsessions), and behavioral intentions (24), and are answered on a scale ranging from 0 to 4, resulting in a total score between 0 and 20. They ask how much of a person's time (total per day), when the drug is not used, is occupied by thoughts, ideas, desires, or impulses related to alcohol and its effects; how frequently these thoughts, ideas, desires, or impulses related to alcohol and its effects occur; how much distress or disturbance these ideas, thoughts, impulses or desire related to alcohol use cause when the person is under withdrawal; how much effort the person has to make to resist these thoughts, ideas, desires, or impulses, or how much energy he/she has to spend to think of something else when they enter the mind under withdrawal; and finally ask about the person's drive to use alcohol.

This scale was applied in the week before the beginning of the real or sham-tDCS treatment (1st measurement), during the treatment over approximately 3-weeks (2nd, 3rd and 4th measurements) and in the week after the end of the brain stimulation protocol (5th measurement).

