### *Procedures*

Those patients who were eligible for study participation according to the inclusion and exclusion criteria described above and agreed to participate in this study signed an informed consent form (Fig. 1). All data were originally acquired from participants participating in a randomized sham-controlled double-blind clinical trial to investigate the efficacy of tDCS treatment of alcohol dependence.

After global physical and clinical examination, subjects were randomly assigned to one of the two intervention groups (sham- and real tDCS) in a 1:1 ratio using a computer-generated block randomization sequence that was kept with the unblinded study coordinator (not involved in recruitment) and only revealed to the co-investigator conducting treatments immediately before the first session.

Craving (5-items OCDS) was measured before and after completion of the treatment and once per week during the three-weeks treatment, resulting in five measurements (Fig. 1). Alcohol use relapses after hospital discharge were verbally obtained from patients, families or caregivers.

Participants and experimenters were blinded for brain stimulation assignments from the beginning of the study protocol up to the end of the 3-months follow-up after the end of sham-tDCS or real tDCS treatment, configuring a double-blind experimental design.

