## Statistical Analysis

We powered the study for a small effect size given our hypothesis that tDCS would be associated with a relevant reduction in craving scores. Thus, assuming a small effect size of 0.3 specified for SPSS in G\*Power 3.1 for a repeated measure (5 measures) within-between interaction analysis of variance (ANOVA) as principal statistical test for the craving analysis with a power of 80%, a two-sided probability of a type I error of 5%, a minimum of 38 subjects would be necessary; however to account for waiving or dropouts expected to be very common in this condition, we increased the estimated sample to approximately 20%, resulting in 45 to 46 subjects (22 to 23 subjects in each group).

Age, patterns of alcohol use and 5-items OCDS were normally distributed according to D'Agostino & Pearson normality test, thus they were analyzed by parametric tests.

Besides the two-way ANOVA (sham-tDCS and tDCS groups as between-subjects factor) with repeated measures (five time-points as within-subjects factor) followed by Bonferroni's multiple comparisons as *post-hoc* test, linear regression analyses were done over craving scores obtained over the respective five time-points for both groups and the slopes of the respective curves were compared using a modified version of the *t* test according to Zar (1984), which is equivalent to analysis of covariance. Additional comparisons between initial and final OCDS scores were done by paired *t* tests for each group, and differences between final and initial scores were compared between sham-tDCS and tDCS groups with unpaired *t* tests. Effect sizes were calculated using Cohen's *d* and corrected by Hedges's  $g_s$  for unpaired and Hedges'  $g_{av}$  for paired *t*-tests (Lakens, 2013).

Age and patterns of alcohol use were compared between groups by unpaired *t*-test. For all other non-parametric data, Chi-square or Fisher tests were used to compare results between sham and real tDCS groups.

A two-tailed p-value of 0.05 or less was considered to indicate statistical significance. SPSS Statistics Base 24.0 (SPSS Inc, USA) and GraphPad Prism 7.0

(GraphPad Software Inc, USA) were employed for statistical analysis and graphic presentations.

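### The supplementary between-arm comparison of initial-to-final OCDS uses raw change scores; adjusting for baseline OCDS would usually, though not always, tighten the estimate (minor, optional)

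*Combined protocol and SAP*

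**What the plan says.** The Statistical Analysis section names the two-group, five-time-point repeated-measures ANOVA interaction "as principal statistical test for the craving analysis with a power of 80"%. Other craving analyses follow, including a comparison of regression slopes over the five time-points by a modified t test, "which is equivalent to analysis of covariance".

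The initial-to-final contrasts come last and are labelled supplementary: "Additional comparisons between initial and final OCDS scores were done by paired" t tests within each group. Between the arms, "differences between final and initial scores were compared between sham-tDCS and tDCS groups with unpaired" t tests.

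On the baseline measurement, the craving assessment section states: "This scale was applied in the week before the beginning of the real or sham-tDCS treatment", as the first of five measurements. Under Procedures, "subjects were randomly assigned to one of the two intervention groups" in a 1:1 ratio.

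Baseline OCDS therefore enters the analysis in three ways: as the first outcome point in the ANOVA, as the first point on the regression lines, and as the subtracted term in the change score. It is never a covariate.

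**The concern.** The principal test is an omnibus interaction over five time-points and does not itself give a single treatment difference from start to end. The between-arm comparison of change does. A raw change score fixes the coefficient on baseline at 1, whatever the data show. ANCOVA estimates that coefficient, which usually leaves less residual variation.

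The mention of analysis of covariance might seem to cover this, but it describes the comparison of slopes. The regressor there is time, not baseline OCDS.

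At stake is the width of the confidence interval for the raw difference in craving change, in a trial of about 22 to 23 patients per arm. Nothing else in the plan depends on it.

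**Working it through.** **The plan's own figure.** The plan gives no number for the change-score test; its only figure is the sample size for the interaction. Take f = 0.3 (SPSS convention), 2 groups, 5 measures, two-sided 5%, and sphericity assumed. Then λ = 0.3² × (N − 2) × 4, with 4 and 4(N − 2) degrees of freedom. At N = 37, λ = 12.60 and power is 0.809. At N = 38 (two equal arms), λ = 12.96 and power is 0.822. The stated minimum of 38 reproduces, and 38 × 1.2 = 45.6 gives the stated 45 to 46. This figure does not involve the change-score test.

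**Inputs for the check.**
- From the Statistical Analysis section: 22 to 23 patients per group, taken as 23 and 22 (N = 45).
- Assumed, because the documents give neither: baseline SD 1, final SD k, baseline-final correlation r. The main case is k = 1 with r from 0.3 to 0.9; k = 0.8 and k = 1.2 are sensitivity cases.

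**Formulas.** Each variance is multiplied by 1/23 + 1/22 = 0.08893.
- Change score: 1 + k² − 2rk, which equals (1 − rk)² + k²(1 − r²).
- ANCOVA: k²(1 − r²) × [1 + 1/(N − 4)]. The bracket is the average cost of estimating the slope: 1 + 1/41 = 1.0244.
- 95% half-width: t quantile × standard error, with 43 df for the change score (2.0167) and 42 df for ANCOVA (2.0181).

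**Worked case, k = 1, r = 0.5.** Change score: 1 + 1 − 1 = 1.000; half-width 2.0167 × √0.08893 = 0.601. ANCOVA: 0.75 × 1.0244 = 0.768; half-width 2.0181 × √(0.768 × 0.08893) = 0.528.

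**Equal SDs, 23 and 22 per arm (half-widths in SD units).**

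| r | Change-score variance | ANCOVA variance | Ratio | Half-width, change | Half-width, ANCOVA |
|---|---|---|---|---|---|
| 0.3 | 1.400 | 0.932 | 0.67 | 0.712 | 0.581 |
| 0.5 | 1.000 | 0.768 | 0.77 | 0.601 | 0.528 |
| 0.7 | 0.600 | 0.522 | 0.87 | 0.466 | 0.435 |
| 0.8 | 0.400 | 0.369 | 0.92 | 0.380 | 0.365 |
| 0.9 | 0.200 | 0.195 | 0.97 | 0.269 | 0.266 |

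The Participants section reports: "Two dropouts occurred after randomization". Taking 22 and 21 per arm (45 less two, an assumption), the half-widths at r = 0.3, 0.5 and 0.7 fall from 0.729 to 0.596, 0.616 to 0.541 and 0.477 to 0.446.

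**Unequal SDs, N = 45.** At r = 0.3, 0.5 and 0.7 the ratios are 0.51, 0.59 and 0.64 for k = 0.8, and 0.78, 0.89 and 0.99 for k = 1.2. At k = 1.2 and r = 0.75, 0.80, 0.85 and 0.90 they are 1.008, 1.021, 1.023 and 1.001, so ANCOVA is slightly worse there. At r = 0.85 its half-width is 0.385 against 0.380.

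**Bound on the loss.** The change-score variance exceeds k²(1 − r²) by (1 − rk)², which is never negative. The ratio therefore cannot exceed 1 + 1/(N − 4): 1.024 at N = 45 and 1.026 at N = 43. It reaches that value only when rk = 1.

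**Simulation.** With 40,000 trials per setting at 23 and 22 per arm, the equal-SD ratios at r = 0.3, 0.5 and 0.7 were 0.667, 0.767 and 0.875. Null rejection was 4.8% to 5.3% for both tests.

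**The case against.** The strongest reply is that the plan contains no error here. The choice is between two valid estimators for a contrast that the plan itself calls additional. Baseline is not ignored either: it is the first point in the principal test and in the slope comparison, and it is subtracted in the change score. All of this stands, and it is why the point is minor.

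A second reply is that the gain rests wholly on assumed values. This also stands. At equal SDs the half-width shrinks by 0.131 SD at r = 0.3 (0.712 − 0.581) but by only 0.015 at r = 0.8 and 0.003 at r = 0.9, and in some configurations it grows slightly.

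A third reply is that an ANCOVA chosen after the data are known adds another result to a scale that already has an interaction test, post-hoc comparisons, a slope comparison and several t tests. That is a real cost, and it limits the ANCOVA to a labelled sensitivity analysis in that situation.

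A reader might also infer that the planned standardised effect size has a needlessly wide interval. That is not shown. The plan corrects Cohen's d to Hedges' g for the unpaired test without saying which SD is the divisor. If it is the SD of change, the usual large-sample variance of g is about 1/n1 + 1/n2 + g²/(2N), which at fixed g does not depend on the baseline-final correlation. The half-widths above apply only to the raw difference.

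**Conclusion.** The point holds as a minor, optional refinement. The supplementary between-arm contrast is a raw change-score t test, no model adjusts for baseline OCDS, and the consequence is confined to the precision of the raw difference. With equal SDs and correlations of 0.3 to 0.9, ANCOVA would reduce the variance by about 33% down to 3%. The least favourable case is a rise of about 2.4% at 45 patients. Where this trial falls in that range cannot be told from the documents.

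A reader might infer that the unadjusted test is biased by chance baseline imbalance, or that the main craving conclusion is weakened. The documents support neither. Under randomised allocation the change-score test is unbiased and holds its level, and the principal test and its sample size are separate from it.

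**What to change.** Estimate the initial-to-final treatment difference by ANCOVA of final OCDS on group with baseline OCDS as covariate, and report the adjusted difference with its 95% CI. The group-by-time interaction stays principal.

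The documents describe recruitment, dropouts and the normality findings in the past tense; of the OCDS and other variables the Statistical Analysis section says "thus they were analyzed by parametric tests". If the data have already been analysed, as this suggests, present the ANCOVA as a labelled post hoc sensitivity analysis beside the planned change-score result, not in its place.

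The cost is one degree of freedom and one more craving result among several. No new data are needed and the sample size does not change.
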